Prepared by: Janssen Research & Development, LLC

EDMS number: EDMS-RIM-36793

THIS APPENDIX APPLIES TO ALL CURRENT APPROVED VERSIONS OF PROTOCOL CNTO148JIA3003 (EDMS-ERI-71227414)

GCP Compliance: This study will be conducted in compliance with Good Clinical Practice, and applicable regulatory requirements.

Confidentiality Statement

The information provided herein contains Company trade secrets, commercial or financial information that the Company customarily holds close and treats as confidential. The information is being provided under the assurance that the recipient will maintain the confidentiality of the information under applicable statutes, regulations, rules, protective orders or otherwise.

Status: Approved, Date: 17 April 2020

COVID-19 APPENDIX

GUIDANCE ON STUDY CONDUCT DURING THE COVID-19 PANDEMIC

It is recognized that the Coronavirus Disease 2019 (COVID-19) pandemic may have an impact on the conduct of this clinical study due to, for example, self-isolation/quarantine by subjects and study-site personnel; travel restrictions/limited access to public places, including hospitals; study site personnel being reassigned to critical tasks.

In alignment with recent health authority guidance, the Sponsor is providing options for study-related subjects management in the event of disruption to the conduct of the study. This guidance does not supersede any local or government guidelines or requirements or the clinical judgement of the investigator to protect the health and well-being of subjects and site staff. If, at any time, a subject's safety is considered to be at unacceptable risk, study drug will be discontinued, and study follow-up will be conducted.

Scheduled visits that cannot be conducted in person at the study site will be performed to the extent possible remotely/virtually or delayed until such time that on-site visits can be resumed. At each contact, subjects will be interviewed to collect safety data. Key efficacy endpoint assessments should be performed if required and as feasible. Subjects will also be questioned regarding general health status to fulfill any physical examination requirement.

Every effort should be made to adhere to protocol-specified assessments for subjects on study drug, including follow up. Modifications to protocol-required assessments may be permitted via COVID-19 Appendix after consultation between the subject and investigator, and with the agreement of the Sponsor (see below).

The Sponsor will continue to monitor the conduct and progress of the clinical study, and any changes will be communicated to the sites and to the health authorities according to local guidance. If a subject has tested positive for COVID 19, the investigator should contact the Sponsor's responsible medical officer to discuss plans for study drug and follow-up. Modifications made to the study conduct as a result of the COVID-19 pandemic should be summarized in the clinical study report.

ADDITIONAL ELEMENTS, WHERE APPLICABLE:

- Certain protocol-mandated visits to the study site may not be possible during the COVID-19 outbreak. Therefore, temporary measures may be implemented if considered appropriate by the Sponsor and investigator to maintain continuity of subject care and study integrity. Certain measures, such as those listed below, may be necessary and should be instituted in accordance with applicable (including local) laws, regulations, guidelines, and procedures:
 - o remote (eg, by phone / telemedicine) or in-person, off-site (eg, in-home) interactions between site staff (or designees) and subjects for study procedures e.g. those related to safety monitoring / efficacy evaluation / study drug storage and administration (including training where pertinent)
 - o laboratory assessments using a suitably accredited local laboratory; for selected measures (eg, urine pregnancy), home testing may be employed
 - o other procedures, eg, imaging, may be conducted at an appropriate facility
 - Missed assessments/visits will be captured in the clinical trial management system for protocol deviations. Discontinuations of study drug and withdrawal from the study should be documented with the prefix "COVID-19-related" in the case report form (CRF).
 - o other relevant study data elements impacted by the pandemic should also be documented / labeled as "COVID-19-related" in CRFs and / or other study systems, as directed by detailed Sponsor guidance. These may include missed / delayed / modified study visits / assessments / dosing, and instances where temporary measures such as those above are implemented.
 - The Sponsor will evaluate the totality of impact of COVID-19 on collection of key study data and additional data analyses will be outlined in study SAP(s).
 - NOTES on COVID-related exclusion:

PKE pharmacokinetics evaluable

q8w every 8 weeks
RBC red blood cell
SAE serious adverse event
SAP statistical analysis plan
SOP Standard Operating Procedure

TB tuberculosis

TNFα tumor necrosis factor alpha VAS visual analogue scale WBC white blood cell

1. INTRODUCTION

This statistical analysis plan (SAP) contains definitions of analysis sets, derived variables, and statistical methods for the analysis of pharmacokinetics (PK), efficacy, safety, and immunogenicity in the CNTO148JIA3003 study.

1.1. Trial Objectives

Primary Objective

The primary objective of this study is to assess the PK following intravenously administered golimumab in subjects (ages 2 to less than 18 years) with polyarticular JIA (pJIA) manifested by ≥ 5 joints with active arthritis despite methotrexate (MTX) therapy for ≥ 2 months.

Secondary Objectives

The secondary objectives of this study are to evaluate IV golimumab in subjects with pJIA with respect to PK, efficacy (relief of signs and symptoms, physical function, quality of life), safety (AEs, SAEs, and assessment of laboratory parameters), and immunogenicity (antibodies to golimumab).

1.2. Trial Design

This is a Phase 3, open-label, single arm, multicenter study to evaluate the PK, safety, and efficacy of IV golimumab in subjects with active pJIA despite current treatment with MTX. Approximately 120 subjects will be enrolled at Week 0 to ensure that approximately 100 subjects remain in the study at Week 52.

All subjects will receive 80 mg/m^2 golimumab (maximum single dose 240 mg [maximum BSA $3.0 \text{ m}^2 \text{ x } 80 \text{ mg/m}^2$]) as an IV infusion (over $30 \pm 10 \text{ minutes}$) at Weeks 0, 4, and $q8w (\pm 3 \text{ days})$ through Week 28 and then $q8w (\pm 1 \text{ week})$ thereafter through Week 52. Subjects will also receive commercial MTX weekly through Week 28 at the same BSA-based dosage (10 to 30 mg/m^2 per week of MTX in subjects with BSA $<1.67 \text{ m}^2$, or a minimum of 15 mg/week in subjects with BSA $\ge 1.67 \text{ m}^2$) as at time of study entry. Subjects who complete the study at Week 52 will have the option to enter into the long-term extension phase of the study (from Week 52 to Week 252). All subjects who complete the Week 244 visit are expected to participate in the safety follow-up visit at Week 252.

Since this is an open-label study with all subjects receiving the same BSA-based dose of IV golimumab, an external Data Monitoring Committee will not be established. Instead, an internal Janssen Data Review Committee (DRC) will be formed in its place.

[figure not shown]
The end of the study is defined as the last follow-up assessment for the last subject in the long-term extension.

Database locks (DBL) are scheduled for Weeks 28, 52 and 252 (Section 1.2.3).

If <50% of the study population achieves an adequate response to the treatment (American College of Rheumatology Pediatric 30% [JIA ACR 30] response) at the Week 28 DBL, the study will be discontinued.

Figure 1 depicts the schematic overview of the study.

Figure 1: Schematic overview of the study

1.2.1. Subject Population

Subjects must meet the inclusion and exclusion criteria of the study.

Subjects must be 2 to less than 18 years of age with a body weight >15 kg at the time of enrollment.

The onset of disease must have been before the subject's 16th birthday, must be of at least 3 months'

duration, and must be active pJIA of one of the following subtypes: rheumatoid factor positive or negative pJIA; systemic JIA with no systemic symptoms for ≥ 3 months but with polyarthritis for ≥ 3 months; extended oligoarticular JIA; enthesitis-related arthritis or polyarticular juvenile psoriatic arthritis (PsA).

Subjects must have ≥ 5 joints with active arthritis as defined by American College of Rheumatology (ACR) criteria at screening and enrollment. Subjects must have active pJIA despite current use of oral, intramuscular, or subcutaneous MTX (for ≥ 2 months before screening) at a weekly dose of ≥ 10 mg/m².

Subjects must have a screening CRP of \geq 0.1 mg/dL with the exception of approximately 30% of the study population.

Screening for eligible subjects will be performed within 6 weeks before administration of the study agent.

1.2.2. Dosage and Administration

The study will have 1 active treatment group.

All subjects will receive 80 mg/m² golimumab (maximum single dose 240 mg) IV infusions at Week 0, Week 4, and q8w (±3 days) through Week 28 and q8w (±1 week) thereafter through Week 244. BSA will be calculated using the Mosteller equation:

BSA $(m^2) = ([height (cm) x weight (kg)]/3600)^{1/2}.$

All infusions will be completed over 30±10 minutes.

In addition, subjects will receive commercial MTX at the same BSA-based dose (10 to 30 mg/m² per week for subjects with BSA <1.67 m² or at least 15 mg/week for subjects with

BSA \geq 1.67 m²) as at time of study entry through Week 28. Absolute dose should remain stable from baseline through Week 28.

1.2.3. Database Locks

Database locks are scheduled at Weeks 28, 52 and 252. The Week 28 and Week 52 database locks will include all data collected up to the Week 28 and Week 52 visits, respectively. The final database lock at Week 252 will include all data collected.

1.3. Statistical Hypotheses for Trial Objectives

No formal hypothesis testing is planned for this study.

1.4. Sample Size Justification

The sample size determination is not based on statistical considerations. For the purpose of determining sample size of this study, the variability of PK in pediatric populations was considered. The goal is to have a sample size that will be sufficient to build a population PK and, if feasible, an exposure-response model. Additionally, a sample size that will provide information about the safety profile of golimumab IV in children was also taken into consideration.

With these considerations, a sample size of approximately 120 subjects has been chosen assuming that if 20 subjects were to drop out or if they do not provide PK samples, a sample size of approximately 100 subjects is thought to be sufficient to build a population PK model, given the sparse sampling of PK time points, as well as provide 1 year of safety data from approximately 100 subjects.

Assuming that inter-subject coefficient of variation (CV%) of concentration is about 50% (moderate – large variation), a sample size of 100 subjects will be able to provide a 95% confidence interval (CI) with the length about 20% of the mean concentration, i.e., 95% CI \approx Mean×(1 \pm 10%).

The table below provides the length of 95% CI of mean concentration using sample size of 100 subjects with various CV% from 30% (small variation) to 70% (larger variation).

CV %	95% CI
30%	Mean×(1± 5.9%)
40%	Mean×(1± 7.8%)
50%	Mean×(1± 9.8%)
60%	Mean×(1±11.8%)
70%	Mean×(1±13.7%)

Table 1: Length of 95% CI with Sample Size 100 Subjects

1.5. Randomization and Blinding

1.5.1. Randomization

All subjects will receive 80 mg/m² golimumab and commercial MTX, therefore randomization of subjects to treatment is not needed.

1.5.2. Treatment Supply and Allocation

Golimumab will be supplied as a sterile liquid for IV infusion at a volume of 4 mL (50 mg, 12.5 mg/mL) in single-use vials. Normal saline will be supplied as a sterile liquid for IV infusion in single-use infusion bags.

Treatment (golimumab vials) allocation will be performed by using a centralized, interactive web response system (IWRS) provided by Parexel International Corporation. After the informed consent has been obtained and the subject has been successfully screened, sites will enroll a subject at Week 0 via the IWRS. Vial numbers will be assigned to the subject. One or more golimumab vials can be assigned at each visit. The assigned vial numbers will be provided via fax to the pharmacist and will be stored electronically in the IWRS database. The IV study agent for infusion will be prepared according to the subject's BSA.

In the event that a vial of treatment is not available at the site or a problem with the vial or vial contents are noted, an alternate vial number will be provided via IWRS to the pharmacist. The sponsor will be alerted in order to promptly address the deficient clinical supply issue. The assignment of the new vial will be recorded in the electronic case report form.

1.5.3. Maintenance of the Blind

This is an open label study with one treatment group, therefore maintenance of blinding is not necessary.

2. GENERAL ANALYSIS DEFINITIONS

2.1. Visit Windows

All scheduled study visits should occur within ± 3 days of the intended visit through Week 28 and ± 1 week from Week 28 through Week 244.

Unless otherwise specified, actual scheduled visits will be used for the summaries and listings over time with no visit windows applied.

For PK analyses, if a subject has an infusion more than \pm 3 days of the scheduled dosing date through Week 28, the concentration data collected between such a dosing visit and the subsequent dosing visit will be excluded from the by-visit data analyses. For the visits after Week 28, if the PK sampling time deviates more than \pm 7 days of the scheduled date, the PK concentration at this visit will be excluded from the by-visit data analyses.

2.2. Pooling Algorithm for Analysis Centers

Data from all investigational centers/sites will be pooled for analyses.

2.3. Analysis Sets

2.3.1. Pharmacokinetics Analysis Set

The pharmacokinetics evaluable (PKE) analysis set includes treated subjects (who received at least 1 infusion) who have sufficient PK samples for analysis.

Pharmacokinetics analyses will be performed using the PKE analysis set.

2.3.2. Full Analysis Set

The full analysis set includes all enrolled subjects who received at least 1 infusion.

This analysis set will be used for efficacy analysis and safety analysis, unless otherwise specified.

2.4. Definition of Subgroups

2.4.1. Subgroups for the Summary of Concentrations

To evaluate the consistency in the concentrations over demographics, baseline characteristics. The subgroups described below are for the concentrations.

The following demographic subgroups will be used for concentration summary:

- a. Age: 2 years to <6 years, ≥ 6 years to <12 years, ≥ 12 years to <18 years
- b. Baseline body weight: quartiles
- c. Baseline BMI: quartiles
- d. Baseline BSA: quartiles
- e. Baseline CRP quartiles, CRP categories (<1.0 mg/dL, $\ge 1.0 \text{ mg/dL}$) and CRP categories (<0.1 mg/dL, $\ge 0.1 \text{ mg/dL}$)

2.4.2. Subgroups for the Summary of Other Efficacy Endpoints

In addition to demographic subgroups of age, gender, race, geographic region, weight, BMI, and BSA the following subgroups will also be used for the summary of JIA ACR30 (Section 5.4.1.1). The subgroups for efficacy analyses include, but are not limited to, the following:

Baseline disease characteristics subgroups

- a. ILAR classification of disease (Systemic onset with polyarticular course with no systemic symptoms, Polyarticular Rheumatoid Factor-negative, Polyarticular Rheumatoid Factor-positive, Oligoarticular extended, Juvenile Psoriatic Arthritis, and Enthesitis-related JIA)
- b. Number of active joints ($<6, \ge 6$ to $<10, \ge 10$)
- c. Number of joints with limited range of motion ($<6, \ge 6$ to $<10, \ge 10$)
- d. CHAQ ($<1, \ge 1$ to $<2, \ge 2$)
- e. CRP (<1.0 mg/dL, and $\ge 1.0 \text{ mg/dL}$ at baseline (Week 0))
- f. CRP (<0.1 mg/dL, and $\ge 0.1 \text{ mg/dL}$ at baseline (Week 0))
- g. Previous joint surgery (yes, no)
- h. Disease duration (<6 months, ≥6 months to <1 year, ≥1 year to <3 years, ≥3 years)

Medication use subgroups:

- a. Prior anti-TNF therapy (yes, no)
- b. Oral corticosteroids (yes, no)
- c. NSAIDs (yes, no)
- d. MTX dose: tertiles
- e. Duration of MTX therapy (<1 year, \geq 1 year to <3 years, \geq 3 years)
- f. Prior DMARDs excluding MTX $(0, 1, 2, \ge 3)$
- g. Concomitant conventional DMARDs use at baseline, excluding MTX $(0, 1, 2, \ge 3)$
- h. Prior biologics, excluding anti-TNFs (yes, no)
- i. Prior JAK inhibitors (yes, no)

3. INTERIM ANALYSIS AND DATA MONITORING COMMITTEE REVIEW

3.1. Interim Analysis

No interim analyses are planned for this study.

3.2. Data Review Committee

An internal DRC will periodically review and assess safety data during the study to ensure subject safety while participating in the study. DRC review will commence when 20 subjects have been enrolled into the study and then will meet at least once annually as well as on an ad hoc basis upon the request of the study team, until the Week 252 DBL. The content of safety summaries, DRC roles and responsibilities, and the general procedures (including

communications) are defined and documented in the DRC Charter. Statistical output will be provided by Parexel International Corporation.

The safety data summary package prepared by Parexel International Corporation includes summaries and listings of all adverse event (AEs), SAEs, infections, infusion reactions, and lab parameter data. Following the review, the DRC will make a formal, written recommendation regarding the conduct of the study to the study team.

4. SUBJECT INFORMATION

Subject information will be summarized for PKE analysis set unless otherwise specified.

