11.1. Subject Information

All subjects who are enrolled in the study will have baseline descriptive statistics provided.

Subject baseline data, demographic and baseline disease characteristics will be summarized. The baseline measurement is defined as the closest measurement taken before the time of the Week 0 study agent administration.

Demographics and subject baseline disease characteristics and prior medication data will be summarized for all subjects who have been enrolled in the study, whether or not they have received study agent administration. Pharmacokinetic data will be summarized for all subjects

who had received at least 1 administration of study agent. Efficacy analyses will be summarized for all subjects enrolled in the study unless otherwise specified. Safety assessments will be summarized for all treated subjects.

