4.2. Disposition Information

The number of subjects screened, enrolled, and treated will be summarized. Subjects who discontinued study agent through Week 28, and 52, and 252, and the reasons for discontinuation will also be summarized. Likewise, subjects who terminated study participation and the reasons for termination will also be summarized.

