7.1.3. General PK Summaries

PK samples for measuring serum golimumab concentrations will be collected from all subjects at the specified visits as shown in the schedule of events of the protocol. Samples will be collected at Weeks 0, 4, 8, 12, 20, 28, 52, 100, 148, 196 and 244. Two samples, one pre-infusion and another post-infusion, will be collected at Weeks 0, 4, and 12. An additional random PK sample for serum golimumab concentration will be collected from all subjects at any time between Weeks 0 and 8 other than at the time of the Week 0, 4 and 8 visits; this sample must be collected at least 24 hours before or after a study agent infusion.

All PK evaluations will be based on the subjects who receive at least 1 infusion of golimumab (PKE analysis set).

No imputation for missing concentration data will be performed. Pre and post infusion serum concentrations will be summarized separately.

The data analysis of serum golimumab concentrations includes the following:

- Summary of serum golimumab concentrations at each visit
- Summary of serum golimumab concentrations at each visit by body weight quartiles.
- Summary of serum golimumab concentrations at each visit by BMI quartiles.

- Summary of serum golimumab concentrations at each visit by BSA quartiles.
- Summary of serum golimumab concentrations at each visit by age (2 to <6 years, 6 to <12 years, 12 to <18 years).
- Summary of serum golimumab concentrations at each visit by CRP quartiles and CRP categories (<0.1 mg/dL, ≥0.1 mg/dL; <1.0 mg/dL, ≥1.0 mg/dL).
- Proportion of subjects without detectable serum golimumab concentration at each visit.
- Summary of serum golimumab concentrations at each visit by antibodies to golimumab status.
- Median serum golimumab concentrations plotted over time.

In addition, the relationship between serum golimumab concentrations and antibody to golimumab status, safety and efficacy may be explored using graphical displays. Median serum golimumab concentrations will be plotted. Box plots of serum golimumab concentrations will be plotted by percentage subjects who achieved JIA ACR 30 responses.

For summary statistics of serum golimumab concentrations, concentration values below the lower limit of quantification will be treated as zero. Once a subject meets one of the following dosing deviation criteria, the subject's data will be excluded from the by-visit data analyses from that point onwards.

Dosing deviation criteria:

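### SAP 4 defaults baseline, disposition, compliance and exposure tables to the PK-evaluable set, which conflicts with Protocol 11.1 for baseline data and has two inconsistent definitions in the SAP

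*SAP*

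**What the plan says.** SAP 4 sets the default for the whole section: "Subject information will be summarized for PKE analysis set unless otherwise specified". Sections 4.1 (demographics and baseline), 4.2 (disposition), 4.3 (compliance) and 4.4 (exposure) name no other population. Neither does the prior-medication paragraph of 4.6. The default is overridden in two places only: protocol deviations (4.5) and concomitant medications (4.6) go to the full analysis set.

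The disposition section asks for two different things. One is a set of counts: "The number of subjects screened, enrolled, and treated will be summarized". The other is the discontinuation table: "Subjects who discontinued study agent through Week 28, and 52, and 252, and the reasons for discontinuation will also be summarized".

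The PKE set has two definitions. SAP 2.3.1: "The pharmacokinetics evaluable (PKE) analysis set includes treated subjects (who received at least 1 infusion) who have sufficient PK samples for analysis". SAP 7.1.3: "All PK evaluations will be based on the subjects who receive at least 1 infusion of golimumab (PKE analysis set". The full analysis set, by contrast, is clear: "The full analysis set includes all enrolled subjects who received at least 1 infusion".

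Protocol 11.1 requires demographics, baseline disease characteristics and prior medication to be "summarized for all subjects who have been enrolled in the study, whether or not they have received study agent administration". The same section takes every subject with at least one administration as the population for PK data.

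**The concern.** There are three problems. First, the SAP moves the baseline and prior-medication tables away from the population that the protocol names, and gives no reason. Second, one label covers two populations, and the narrower one depends on the word *sufficient*, which the SAP does not define. Two programmers could build different denominators, and the threshold could be settled after the data are seen. Third, under the narrower definition, presence in the discontinuation table depends on having supplied PK samples, which stopping early limits.

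This is a single-arm, open-label study without hypothesis testing, so its descriptive tables carry the interpretation. A reader needs to know who entered, who stopped and why. If PKE differs from the full analysis set, the baseline table also describes a different group from the efficacy and safety tables.

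**Working it through.** **Which set applies where**

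| Summary | Set under the SAP | Set under Protocol 11.1 |
|---|---|---|
| Demographics, baseline (4.1) | PKE by default | All enrolled |
| Prior medication (4.6) | PKE by default | All enrolled |
| Discontinuation and reasons (4.2) | PKE by default | Not stated |
| Compliance, exposure (4.3, 4.4) | PKE by default | Not stated |
| Protocol deviations (4.5) | Full analysis set | Not stated |
| Concomitant medication (4.6) | Full analysis set | Not stated |

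The explicit switches in 4.5 and 4.6 show that the default was overridden where another set was wanted. Silence elsewhere therefore leaves PKE in force. The counts of subjects screened, enrolled and treated cannot be PKE counts by their nature, so the default does not work for part of 4.2.

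**What each PKE definition does.** Under 7.1.3, PKE is every treated subject, which is the full analysis set, and no treated subject is lost. Under 2.3.1, PKE is the treated subjects less those without sufficient samples, a number that cannot be fixed from the text.

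**The plan's own figure.** SAP 1.4 plans about 120 subjects and allows for 20 who drop out or give no PK samples, leaving 100. The share is 20/120 = 16.7%, and 100/(1 − 20/120) = 120, so the figure reproduces.

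**Illustration.** Assume N = 120 treated and D = 20 discontinuing, with k of those 20 lacking sufficient samples. The documents give no value for k. They also give the 20 as dropout *or* missing samples, so treating all 20 as discontinuations is an assumption too.

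- Full analysis set: D/N = 20/120 = 16.7% for every k.
- PKE under 2.3.1: (D − k)/(N − k).

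| k | PKE table |
|---|---|
| 0 | 20/120 = 16.7% |
| 1 | 19/119 = 16.0% |
| 2 | 18/118 = 15.3% |
| 5 | 15/115 = 13.0% |
| 10 | 10/110 = 9.1% |
| 20 | 0/100 = 0% (extreme bound) |

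**How large k could be.** Protocol 9.3.3 schedules a pre- and a post-infusion sample at Week 0 and one random sample between Weeks 0 and 8. Protocol 10.2 adds a sample about 8 weeks after the last infusion for subjects who stop infusions but stay in the study. A subject who stops after one infusion and stays in follow-up is therefore scheduled for up to three post-dose samples. This points to a small k, although the number of samples that suffices is not stated.

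**What other tables recover.** SAP 6 uses the full analysis set. Section 6.2 gives AEs leading to discontinuation, deaths, the proportion receiving each scheduled infusion, cumulative dose, average follow-up and average number of infusions. It does not give non-AE reasons for stopping. These can dominate: in the sponsor's earlier subcutaneous study in pJIA (Protocol 1.1.2.2), 19 subjects stopped through Week 16, of whom 14 stopped for lack of efficacy and 1 withdrew consent. That is 15/19 = 79% not due to AEs.

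**The case against.** The strongest reply is that nothing need be lost. SAP 7.1.3 and the PK population in Protocol 11.1 both point to all treated subjects. On that reading baseline, efficacy and safety share one treated population. Even under 2.3.1 the sampling schedule makes large exclusions unlikely. Any gap between the treated count and the PKE count would be visible, and exposure and AE-related stopping are reported on the full analysis set anyway. No primary or major secondary result depends on the denominator used in SAP 4.

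Most of this stands, and it limits the size of the problem. It does not remove it. SAP 2.3.1 is the formal definition and says something different from 7.1.3. A visible gap in counts would not show why the missing subjects stopped. On either definition, the baseline and prior-medication tables leave out enrolled but untreated subjects, whom the protocol includes.

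A reader might infer more than the documents support:

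- **That early dropouts will disappear from the discontinuation table.** This can happen only under 2.3.1, and only to subjects who fall short of an unstated sample requirement.
- **That the table could show no discontinuations.** The 0% case needs all 20 to lack sufficient samples, which is implausible given the schedule.
- **That all of SAP 4 is on PKE.** Deviations and concomitant medications are not.

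**Conclusion.** The concern holds as a conflict between documents and a conflict within the SAP, and it should be corrected. For demographics, baseline disease characteristics and prior medication, the SAP contradicts Protocol 11.1 whichever PKE definition is used. For disposition, the effect depends on that definition: none for treated subjects under 7.1.3, and under 2.3.1 a likely small loss that falls mainly on non-AE reasons for stopping. The figures of 16.7%, 13.0% and 9.1% show direction and scale under assumed overlaps of 0, 5 and 10. They are not predictions. The exposure tables matter less, because SAP 6.2 already covers most of that content on the full analysis set.

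**What to change.** - **SAP 4:** summarize demographics, baseline characteristics, prior medication and disposition for all enrolled subjects. Protocol 11.1 already requires this for the first three. Summarize compliance and exposure for the full analysis set, in line with SAP 6.
- **SAP 2.3.1 and 7.1.3:** adopt one PKE definition with an explicit minimum sample requirement. If it is narrower than the PK population in Protocol 11.1 (at least one administration), say so and give the reason.
- **Use of PKE:** restrict it to PK analyses.

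The cost is SAP wording and a population flag in the table shells. No new data are needed. Subjects are enrolled at Week 0 through the IWRS (SAP 1.5.2), so enrolled and treated numbers should nearly coincide.
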